
Statistical Methods
	
Descriptive statistics (mean, standard deviation, median, minimum, and maximum values) will be tabulated for the study population. Subject disposition, demographic and Baseline characteristics, extent of exposure and study termination/withdrawal information will be presented. Descriptive statistics will be presented for each of the

	
evaluable safety and efficacy parameters for change from Baseline as well as value at each time point. Adverse event information will be summarized by age group and narratives were used in presentation of the data for safety monitoring. Serious adverse events (SAEs) will be summarized similarly and narratives presented. Clinical laboratory values will be summarized by time point, subject, and age group. Values and changes from baseline at each time point will be tabulated.

--	------------------------------------------------------------------------------------------------------------------------------------------------------------------------------------------------------------------------------------------------------------------------------------------------------------------------------------------------------------------------------------------------------------------------------------------------------------------------------------------------------

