### **3.5 End-of-Study (EOS) Phase (Visit 9, Week 16, Days 112±4)/Early Termination**

The EOS Visit (Visit 9) will be conducted 4 weeks following the last scheduled treatment Visit. Subjects will report to the clinic in the morning following a 10-hour fast. The following procedures will be performed:

- Review of concomitant medication;
- Complete PE, only if the investigator deems it necessary;
- Measurement of weight;
- Collection of unused ORMD-0801 medication;
- 12-Lead ECG, only if the investigator deems it necessary;
- Measurement of vital signs (SBP/DBP, heart rate and oral temperature), only if the investigator deems it necessary;
- Fasted blood samples will be collected for clinical laboratory evaluations (see [Section 6.5.5.1](#) for a complete list of tests performed):
  - Serum Chemistry including liver function tests (LFTs) and blood lipids;
  - Hematology;
- Measurement of fasting blood glucose and fasting insulin for HOMA estimates;
- Review/Collect subject diaries for self-monitored fasting morning blood glucose;
- HbA1c;
- Adiponectin test;
- AEs/SAEs assessment.

Patients who are discontinued early from the study will complete the EOS evaluations at the time of early discontinuation.

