### 6.5.5 Clinical Laboratory Tests

Blood for clinical safety laboratory assessments will be collected and processed using standard procedures at Screening and on Visits 3, 6, 7, 8 and 9 and on any unscheduled visit if the investigator deems it necessary, as indicated in [Table 1](#). A local laboratory will perform all clinical laboratory tests. In the event of abnormal clinical laboratory values, the Investigator will make a judgment whether or not the abnormality is clinically significant.

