### 8.1 Sample Size

Up to 36 patients with NASH and Type 2 DM will be randomized to complete approximately 30 in this multi-center exploratory study. Subjects will be enrolled at 2 sites in Israel and 3 sites in the USA.

The treatment regimen will consist of a soft gelatin capsule containing 8 mg insulin, and 75 mg SBTI. Patients will take one capsule in the morning and one capsule at night, daily, or matching placebo, based on their randomized schedule.

The size of the study population was determined by reviewing the literature for pilot studies and was found to be sufficient to show trends of reducing liver fat content by MRI-PDFF images and CAP-Fibroscan. This study is not powered for statistical significance.

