### 8.2.2 Laboratory Evaluations

Individual clinical safety lab (hematology, serum chemistry and serology) values will be listed by visit and summarized using descriptive statistics as appropriate (i.e., mean, median, range, and standard deviation for continuous data and frequency for categorical data). Individual change from baseline (Screening) in laboratory values will be calculated and summarized descriptively. Shift tables from baseline (Screening) to post-dose (Visit 8) will also be produced for the laboratory assessments based on the categories of Low, Normal, and High. A clinically significant change from baseline will be recorded as an AE if deemed appropriate by the Investigator.

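### The categorical lab shift table stops at Visit 8, so it misses abnormalities that resolve before Week 12 and subjects with no Visit 8 sample; a worst on-treatment shift should be added

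*Combined protocol and SAP*

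**What the plan says.** Section 8.2.2 plans four things for laboratory data.

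- Listings and by-visit summaries: "Individual clinical safety lab (hematology, serum chemistry and serology) values will be listed by visit and summarized using descriptive statistics as appropriate".
- Changes: "Individual change from baseline (Screening) in laboratory values will be calculated and summarized descriptively".
- A categorical display using Low, Normal and High: "Shift tables from baseline (Screening) to post-dose (Visit 8) will also be produced for the laboratory assessments".
- A route into the adverse event tables: "A clinically significant change from baseline will be recorded as an AE if deemed appropriate by the Investigator".

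The synopsis adds "Clinical laboratory values will be summarized by time point, subject, and age group", and says that values and changes will be tabulated per time point.

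Samples are taken more often than the shift table uses them. Section 6.5.5 schedules safety labs "at Screening and on Visits 3, 6, 7, 8 and 9 and on any unscheduled visit" when the investigator sees a need. For subjects who leave, Section 3.5 says "Patients who are discontinued early from the study will complete the EOS evaluations at the time of early discontinuation", and Table 1 places early termination in the Visit 9 column. Section 8.2.7 rules out filling in missing safety values.

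**The concern.** Safety is the primary objective and endpoint, and clinical laboratory results are a named safety assessment. A reader who wants to know how many subjects moved out of the normal range on ORMD-0801, compared with placebo, will turn to the shift table. As defined, it answers a narrower question: who was outside the range at Week 12, among those sampled at Week 12.

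Three groups are handled poorly. A subject whose liver enzymes rise at Week 4 or Week 8 and settle by Week 12 counts as unchanged. A subject who leaves before Week 12 has no row, although Section 4.3 intends every randomized and treated subject to be in the safety analyses. A subject stopped under the glucose rules of Section 3.7 who keeps attending has a Visit 8 value, but it was drawn off study drug and is still labelled post-dose.

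The plan is also uneven. For adverse events, Section 8.2.1 reports each subject's greatest severity. Laboratory values have no comparable worst-case rule.

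**Working it through.** The plan states no figure for this point that could be reproduced, so the check is a count of draws, a count of subjects and a comparison of displays.

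**Draws.** The first randomized dose is given at Visit 3, and the samples at that visit precede it (Section 5.3.1; Table 1, footnote 5). Scheduled safety labs after that dose fall at Visit 6 (Week 4), Visit 7 (Week 8), Visit 8 (Week 12) and Visit 9 (Week 16).
- Scheduled post-dose draws used by the shift table: 1 of 4.
- Scheduled on-treatment draws (Visits 6, 7 and 8) used: 1 of 3. Weeks 4 and 8 do not feed it.

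**Subjects.** Section 8.1 says "Up to 36 patients with NASH and Type 2 DM will be randomized to complete approximately 30", and Section 5.2 gives 2:1 allocation.
- Non-completers: 36 − 30 = 6, and 6/36 = 16.7%.
- Arm sizes: 36 × 2/3 = 24 active and 36 × 1/3 = 12 placebo.
- If dropout is equal by arm (assumed): 24 × 6/36 = 4 active and 12 × 6/36 = 2 placebo.
- If all six fall in one arm: 6/24 = 25% of active or 6/12 = 50% of placebo.

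This treats every non-completer as lacking a Visit 8 lab. It is therefore an upper figure on the plan's own numbers: a subject lost between Visits 8 and 9 has a Visit 8 lab but may not count as a completer.

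**Illustration of what the table would show.** The documents give no rate of abnormality. Assume that a proportion *p* of the 24 active subjects ever becomes abnormal on treatment, that a share *s* of those are still abnormal at Week 12, and that missing Visit 8 is unrelated to abnormality. The expected number ever abnormal is 24*p*. The expected number shown in the table is 24 × *p* × *s* × 30/36.
- *p* = 5%, *s* = 25%: 1.2 ever abnormal, 0.25 shown.
- *p* = 10%, *s* = 50%: 2.4 ever abnormal, 1.0 shown.
- *p* = 20%, *s* = 50%: 4.8 ever abnormal, 2.0 shown.
- *p* = 20%, *s* = 100%: 4.8 ever abnormal, 4.0 shown.

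**Do the other displays give the missing count?**
- By-visit means, medians, ranges and standard deviations can reveal an extreme value, but not how many subjects were ever abnormal.
- Listings hold every value, but a reader would have to count by hand.
- Changes per time point describe each visit separately and do not link visits within a subject.
- The synopsis mentions a summary by subject but defines no abnormality count.
- The adverse event tables count subjects by treatment group, but a laboratory change enters them only at the investigator's discretion.

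None supplies, by arm, the number of subjects who ever became abnormal on treatment.

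**Subjects stopped under Section 3.7.** After either glucose rule is met, study drug stops but visits continue (where possible, after the high-glucose rule). Those stopped for high glucose are also offered rescue medication. Their Visit 8 value then reflects a period off drug, and possibly on rescue.

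**The case against.** The strongest reply is that no laboratory data are lost and that only one table is affected. That is right. A reader might infer that Week 4 and Week 8 abnormalities, and the labs of early leavers, are absent from the safety reporting altogether. The documents do not support this: every value is listed by visit, changes are tabulated at each time point, and labs are drawn at early discontinuation.

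It is also tempting to call the shift table the primary safety summary. Nothing in the plan gives it that status, and Section 8.2.2 presents it as an additional display. Section 8.2.1 also tabulates treatment-emergent events by subject and separately summarizes those leading to withdrawal. A subject withdrawn for a laboratory abnormality judged to be an adverse event is therefore shown there.

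A third tempting inference is that the table is biased toward showing no shift. A missing Visit 8 value removes the subject from numerator and denominator alike. Bias in the percentages among those sampled needs dropout to be related to laboratory findings. Section 4.3 makes that possible, since an adverse event can end participation, but it lists many other reasons and the documents give no rate of lab-driven withdrawal. The bias is plausible and not shown.

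Two further objections stand as limits on the remedy. All subjects have type 2 diabetes and many may enter with raised liver enzymes. A subject already High at baseline stays High to High whichever endpoint is used, so worsening there must be read from the changes from baseline. Unscheduled draws are triggered by events, so including them makes a worst-value table look less favourable.

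Finally, with about 24 and 12 subjects, someone could count from the listings. That is true, but an unplanned hand count is a weaker basis for a primary safety conclusion than a prespecified table.

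**Conclusion.** The point holds as a reporting gap in one display. The shift table draws on 1 of 3 scheduled on-treatment samples. It leaves out at most about 6 of 36 subjects (17%) for want of a Visit 8 lab, and it mixes off-drug values with on-drug ones when a subject stopped under Section 3.7 keeps attending. The 17% rests on two approximate figures and on reading non-completion as no Visit 8 lab. The plan states neither a dropout rate nor a split by arm, so 4 of 24 active is only the equal-dropout case. The number of transient abnormalities missed cannot be estimated from the documents.

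No efficacy result and no sample size depends on this. It merits a change because safety is the primary endpoint, the arms are small enough for one or two subjects to matter, and the better table uses data already collected.

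**What to change.** In Section 8.2.2, or in the statistical analysis plan to which Section 8 leaves further detail, add a shift table by treatment arm from baseline to the worst on-treatment value, with the highest and the lowest value tabulated separately. Specify that:

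- it includes every safety-population subject with any laboratory value after the first randomized dose, and shows that denominator;
- it uses Visits 6, 7 and 8 and early-termination draws;
- it includes unscheduled draws with a flag, so that the result can be read with and without them;
- it states how draws taken after study drug has stopped are classed, both for early-termination samples and for subjects who keep attending under Section 3.7.

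Keep the Visit 8 shift as a second table, and keep the change-from-baseline summaries for subjects already outside the range at baseline. The choice of baseline visit is a separate matter: Section 3.1 labels Visit 3 as baseline while Section 8.2.2 uses Screening. Both shift tables should follow whichever is settled.

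The cost is a few lines of wording and one additional programmed table, with no new visits or samples. The downside is a table that looks slightly less favourable, because transient abnormalities and event-triggered draws are counted.

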### **2.3 Primary Endpoint**

- To evaluate safety of ORMD-0801 in patients with nonalcoholic steatohepatitis (NASH) and type 2 DM.

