#### Inclusion Criteria

1. Male or female aged 18-70 years.
2. BMI  $\geq 25$ .
3. Known type 2 DM according to American Diabetic Association (one of the three needed): Fasting Plasma Glucose  $\geq 126$  mg/dl or 2h postprandial (PG) following 75g OGTT  $\geq 200$  mg/dl or HbA1c  $> 6.5\%$  or on treatment with metformin only or metformin in addition to no more than two of the following medications sulfonylurea, DPP-4 inhibitors, GLP-1 receptor agonists, Thiazolidinediones (TZDs).
4. Diagnosis of NAFLD by non-invasive determination of hepatic steatosis grade S1, defined as hepatic steatosis  $> 8\%$ , by MRI- PDFF and CAP FibroScan  $\geq 238$  dB/m.
5. Liver enzyme abnormalities: ULN  $\leq 5$  times.
6. Fibrosis score  $1 \leq F \leq 3$  as defined by FibroScan measurement (Liver stiffness measurement, LSM) of  $6 \leq \text{LSM} \leq 12$  kPa.
7. Signature of the written informed consent.
8. Negative serum pregnancy test at study entry for females of childbearing potential.
9. Women of childbearing potential must have a negative urine pregnancy test result prior to the start of the run-in period and initiation if active dosing. Males and females of childbearing potential must use two methods of contraception (double barrier method), one of which must be an acceptable barrier method from the time of screening to the last study visit (22 weeks). Barrier methods of contraception include male condoms plus spermicide, diaphragm with spermicide plus male condom, and cervical cap with spermicide plus male condom. Acceptable methods of birth control include abstinence, oral contraceptives, surgical sterilization, vasectomy, the contraceptive patch, and the contraceptive ring. If a subject is not usually sexually active but becomes active, he or his partner should use medically accepted forms of contraception. Sperm donations will not be allowed for the duration of the study and for 90 days after the last dose of study drug.  
Females of non-childbearing potential are defined as postmenopausal who a) had more than 24 months since last menstrual cycle with menopausal levels of FSH (FSH Level  $> 40$ ), b) who are surgically menopausal (surgical sterility defined by tubal occlusion, bilateral oophorectomy, bilateral salpingectomy or hysterectomy).

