## 4.2 Exclusion Criteria

Subjects who meet any of the following criteria must be excluded from the study:

1. Patients with active (acute or chronic) liver disease other than NASH (e.g. viral hepatitis, genetic hemochromatosis, Wilson disease, alpha-1 antitrypsin deficiency, alcohol liver disease, drug induced liver disease) at the time of enrolment.
2. ALT or AST > 5 times ULN.
3. Abnormal synthetic liver function (serum albumin  $\leq$ 3.5gm%, INR >1.3).
4. Known alcohol and/or any other drug abuse or dependence in the last five years.
5. Weight >120 Kg (264.6 lbs.).
6. Known history or presence of clinically significant, cardiovascular, gastrointestinal, metabolic (other than diabetes mellitus), neurologic, pulmonary, endocrine, psychiatric, neoplastic disorder or nephrotic syndrome.
7. History or presence of any disease or condition known to interfere with the absorption, distribution, metabolism or excretion of drugs including bile salt metabolites (e.g. inflammatory bowel disease (IBD), previous intestinal (ileal or colonic) operation, chronic pancreatitis, celiac disease or previous vagotomy.
8. Weight loss of more than 5% within 6 months prior to enrolment.
9. History of bariatric surgery.
10. Uncontrolled blood pressure BP  $\geq$ 150/ $\geq$ 95.
11. Non type 2 DM (type 1, endocrinopathy, genetic syndromes etc.).
12. Patients with HIV.
13. Daily alcohol intake >20 g/day (2 units/day) for women and >30 g/day (3 units/day) for men.
14. Treatment with anti-diabetic medications other than metformin and more than-two of the following medications sulfonylurea, DPP-4 inhibitors, GLP-1 receptor agonists, TZDs
15. Metformin, fibrates, statins, not provided on a stable dose in the last 6 months.
16. Patients who are treated with valproic acid, Tamoxifen, methotrexate, amiodarone.
17. Chronic treatment with antibiotics (e.g. Rifaximin).
18. Homeopathic and/or Alternative treatments. Any treatment must be stopped before the screening period.
19. Uncontrolled hypothyroidism defined as Thyroid Stimulating Hormone >2X the upper limit of normal (ULN). Thyroid dysfunction controlled for at least 6 months prior to screening is permitted.
20. Patients with renal dysfunction: eGFR < 40 ml/min.
21. Unexplained serum creatinine phosphokinase (CPK) >3X the upper limit of normal (ULN). Patients with a reason for CPK elevation may have the measurement repeated prior to enrolment; a CPK retest > 3X ULN leads to exclusion.

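### The Low/Normal/High laboratory shift table cannot register ALT or AST worsening in subjects who enter above ULN, and no planned output counts large enzyme rises by arm

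*Combined protocol and SAP*

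**What the plan says.** Safety is the primary endpoint; Section 2.3 words it as "To evaluate safety of ORMD-0801 in patients with nonalcoholic steatohepatitis (NASH) and type 2 DM".

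For laboratory values, Section 8.2.2 plans four things:

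- Values "will be listed by visit and summarized using descriptive statistics as appropriate"; the statistics named for continuous data are mean, median, range and standard deviation.
- "Individual change from baseline (Screening) in laboratory values will be calculated and summarized descriptively".
- One categorical display, of which the section says "Shift tables from baseline (Screening) to post-dose (Visit 8) will also be produced"; its scale is "based on the categories of Low, Normal, and High".
- A clinically significant change becomes an adverse event if the investigator thinks that appropriate. No numeric trigger is given.

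The synopsis adds minimum and maximum values, change from baseline and value at each time point, and laboratory summaries by time point, subject and age group. Neither place says that the laboratory tables are split by treatment arm.

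On entry, Section 4.1 (criterion 5) reads "Liver enzyme abnormalities: ULN" followed by an upper bound of 5 times, with no lower bound. Section 4.2 (criterion 2) removes only subjects with "ALT or AST > 5 times ULN". Section 6.5.5 has the safety laboratory tests drawn "at Screening and on Visits 3, 6, 7, 8 and 9", and at unscheduled visits if the investigator sees a need.

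**The concern.** The top category of the shift table begins at the ULN, yet the trial admits subjects who are already there. For them the scale is at its ceiling before the first dose, and no later enzyme rise, however steep, can move them to a worse cell. A trivial crossing of the ULN by a subject who enters Normal does count. For ALT and AST the table therefore flags some small changes and is blind to some large ones.

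This matters because the population has liver disease, the primary question is safety, and Section 8.2.1 plans no inferential comparison of adverse events. The descriptive tables are the safety evidence. A reader who wants to know how many subjects per arm had a substantial enzyme rise finds no planned table with the answer.

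**Working it through.** The plan gives no figure to reproduce here. The check applies its classification rule to values that entry allows.

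**Inputs.** Three categories, Screening to Visit 8 (Section 8.2.2). Entry limit of 5 times ULN (Sections 4.1 and 4.2). About 36 subjects randomized 2:1 (Section 5.2), with about 30 expected to complete (Section 8.1). High is taken to mean above ULN, which the text does not spell out.

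**Step 1: classify illustrative pairs (in multiples of ULN).**

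| Screening | Visit 8 | Fold rise | Planned table |
|---|---|---|---|
| 1.2 | 3.6 | 3.6/1.2 = 3.0 | High to High |
| 1.5 | 9 | 9/1.5 = 6.0 | High to High |
| 2 | 10 | 10/2 = 5.0 | High to High |
| 3 | 15 | 15/3 = 5.0 | High to High |
| 5 | 20 | 20/5 = 4.0 | High to High |
| 0.9 | 1.05 | 1.05/0.9 = 1.17 | Normal to High |

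Only the smallest change registers.

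**Step 2: how many subjects this could affect.** Active: 36 × 2/3 = 24. Placebo: 36 − 24 = 12. The share entering High is not stated, so it is assumed over a range:

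| Assumed share entering High | Active, no upward shift possible | Placebo |
|---|---|---|
| 25% | 6 of 24 | 3 of 12 |
| 50% | 12 of 24 | 6 of 12 |
| 75% | 18 of 24 | 9 of 12 |
| 100% | 24 of 24 | 12 of 12 |

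The last row applies if criterion 5 is read as requiring an abnormality. If it is only an upper limit, any lower share is possible.

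**Step 3: what the other outputs would show.** Suppose one of 24 active subjects goes from 2 to 10 times ULN and the other 23 do not change.

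- Mean change: (10 − 2)/24 = 0.33 times ULN. With 20 active completers (30 × 2/3) it is 8/20 = 0.40.
- Maximum change: 10 − 2 = 8 times ULN.
- SD of change: √(64/24) ≈ 1.6 times ULN.
- The individual listing shows both values.

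The mean alone is a weak signal, but the maximum and the SD in the same summary are conspicuous. What they do not give is the number of subjects with a rise of a given size.

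**Step 4: timing.** The table uses Visit 8 only, so it misses a peak at Visit 6 or 7 that has receded by Visit 8. Section 8.2.7 allows no substitution for missing data, so a subject with no Visit 8 sample drops out of the table. On the planning figures, up to 36 − 30 = 6 subjects could be in that position if non-completers have no Visit 8 sample.

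**The case against.** The strongest reply is that this is a descriptive, exploratory study of 36 subjects in which little can stay hidden. Listings cover every value at every visit and are short enough to read in full. The ranges and maxima would expose an extreme value, and the synopsis also promises summaries by subject. Section 7.2 counts abnormal laboratory findings among adverse events, and Section 8.2.1 tabulates treatment-emergent events by arm and severity, counting subjects. Section 8 also defers further detail to a statistical analysis plan, and the document contains no separate text of that kind.

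Much of this stands, and it rules out several stronger readings. A reader might infer that a large rise would escape the planned summaries altogether; Step 3 shows that the maximum, the SD and the listing would carry it. A reader might take the shift table for the only subject-level view of laboratory safety; the listings and the synopsis contradict that. A reader might also assume that every subject enters High; criterion 5 has no lower bound and does not settle this. Finally, the shift table does work for subjects who enter with normal enzymes, and new elevations in them matter too.

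The reply does not supply the missing count. A range shows one extreme, not how many subjects worsened, and a listing leaves the counting to the reader. The adverse-event table depends on the investigator's judgement, so it is not a systematic tally of laboratory values. CTCAE grading is stated for adverse events, not for laboratory results. The small sample makes a table of counts sparse, but a descriptive study still needs a scale on which worsening can appear.

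**Conclusion.** The concern holds as a limitation of the planned display. For subjects who enter with ALT or AST above ULN, the shift table cannot show worsening. Nothing in Section 8 or the synopsis systematically counts, by arm, the subjects with large enzyme rises. It does not follow that the safety data are lost or that the primary evaluation fails.

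The size depends on the unstated share entering High: 6 to 24 of 24 active subjects and 3 to 12 of 12 placebo subjects over an assumed 25% to 100%. The conclusion assumes that High means above ULN. It is limited to the text available, since a separate analysis plan could add thresholds. The change is a cheap improvement to the display of the primary endpoint and is worth making before unblinding.

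**What to change.** Amend Section 8.2.2, or specify in the statistical analysis plan:

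1. For ALT and AST, and for a complete liver display also alkaline phosphatase and total bilirubin, replace Low/Normal/High with a few multiple-of-ULN bands, for example ≤1, >1–3, >3–5 and >5 times ULN, with a separate count above 10. All five High-to-High pairs in the working would then register as upward shifts.
2. Tabulate by treatment arm, from one stated pre-dose value to the worst post-dose value over Visits 6, 7, 8, 9 and unscheduled visits. The pre-dose value needs naming because Section 8.2.2 uses Screening while Section 3.1 labels Visit 3 as baseline.
3. Add by-arm counts of subjects whose worst value is at least 2 times, and at least 3 times, their own pre-dose value and also above ULN. The second condition keeps out changes wholly within normal, such as 0.4 to 0.8 times ULN.
4. Keep Low/Normal/High for the other analytes.

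These are tabulation cut-points only; no clinical rule changes. Section 6.5.5 uses local laboratories, so multiples of ULN would also put results on a common scale if reference ranges differ between sites, which the text does not say.

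The cost is revised wording and one or two extra tables from data already collected. The downside is sparse cells: four bands give 4 × 4 = 16 cells per analyte and arm, for 24 and 12 subjects.
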